**b) Adherence to CAB LA PrEP schedule**

- Proportion of days covered by CAB LA PrEP in the 12 months following initiation: number of days covered by CAB LA PrEP divided by the number of days in the observation period

Follow-up will be censored at first of:

- a) 12 months after index date
- b) Loss to follow-up
- c) Death
- d) Study end

Coverage by LA PrEP will be determined based on the duration of days covered by the medication, according to the label.

- 1st injection: coverage = 37 days (30 days of coverage + 7-day injection window)
- Subsequent injections: coverage = 67 days (60 days of coverage + 7-day injection window)

Each calendar day will only be counted once, even if there is an overlap between coverage from the prior injection and date of the next injection.

- **Complete versus incomplete initiation:**

- Among all Veterans with  $\geq 1$  CAB LA injection:

→ Complete initiation (2nd injection received within 67 days following the 1st injection)

- 2nd initiation injection on time: 2nd injection between 23 and 37 days following the first injection
- 2nd initiation injection late: 2nd injection between 38 and 67 days following the first injection

→ Incomplete initiation: >67 days without injection following the first injection

- Among incomplete initiators

Any additional injection(s) >67 days after the 1st injection (Yes/no)

If yes:

- o Timing of the 1st additional injection after the last injection of the “incomplete initiation” (interval in days, number with interval of 68-97 days and interval >97 days)
- o Complete versus incomplete reinitiation
- o Interval between the first two reinitiation injections ( $\leq 37$ ; 38-67, 68-97, 98-127;  $\geq 128$  days apart)

• **Timing of CAB LA PrEP maintenance injections:** among complete initiators with at least one maintenance injection

Determined based on the time between initiation injections (Table 3)

- Total number of maintenance injections per individual
- All on time
- Any late maintenance injection (short delays not requiring reinitiation, long delays requiring reinitiation): number of short and long delays, number of individuals with 1, 2, 3 or more short delays, number of individuals with 1, 2, 3 or more long delays, median duration of short and of long delays

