**Table 3:** Timing of CAB LA PrEP maintenance injections, among complete initiators with  $\geq$  maintenance injection

Dosing pattern	Timing of maintenance injections (following previous injection)
On-time	53-67 days
Late	68-127 days
Short delay not requiring reinitiation	68-97 days
Long delay requiring reinitiation	98-127 days
Discontinuation	>127 days without injection

◆ **Patterns of PrEP use (Objective 3.4)**

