**b) CAB LA PrEP: among complete initiators with at least one maintenance injection**

- Total number maintenance injections administered during first period of CAB LA PrEP use (overall and by person)

- Total follow-up time for complete CAB LA initiators with at least one maintenance injection (from first CAB LA PrEP injection to study end, loss to follow-up, death or HIV acquisition, whatever comes first)
- Discontinuation: number of individuals discontinuing CAB LA PrEP and number of individuals resuming LA PrEP injections (additional CAB LA or LEN LA injections after discontinuation and time between the last injection prior discontinuation and the first injection post-discontinuation) or oral PrEP
- Oral bridging between discontinuation of CAB LA injections and resumption of CAB LA injections
- Months on regimen until first censoring (first period of CAB LA PrEP use)  
Calculated as: days from first initiation injection to censoring (study end, loss to follow-up, death, HIV acquisition, discontinuation)
- Cumulative months on regimen across all CAB LA PrEP use (including additional injections after discontinuation)
  - Continuous time on CAB LA PrEP will be calculated as:
    - If no discontinuation: days from first initiation injection to censoring (study end, loss to follow-up, death, HIV acquisition)
    - If discontinuation: days from first initiation injection to discontinuation date (i.e., 127 days after last injection)
  - Among individuals with additional injections after discontinuation, the cumulative months on CAB LA regimen will be calculated across all episodes of continuous CAB LA PrEP use
  - Individuals with incomplete initiation of their first period of CAB LA PrEP use will be excluded from this analysis even if they have additional injections after incomplete initiation
- On CAB LA PrEP at timepoints of interest – among CAB LA users with no discontinuation and among CAB LA users with discontinuation
  - 12 months: injection received between  $\geq 238$  to  $\leq 365$  days after index (up to 127 days before the 12-month mark)
  - 24 months: injection received between  $\geq 603$  to  $\leq 730$  days after index (up to 127 days before the 24-month mark)
  - Study end: injection received up to 127 days before or on study end date
- ◆ **HIV testing & STI testing/screening during first period of PrEP use (Objectives 3.5)**
  - HIV testing

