    - Incidence proportion and incidence rate of HIV testing between the start of PrEP and the first discontinuation
    - Timing of HIV tests:
      - Oral PrEP: on-schedule testing defined as receiving an HIV test  $\leq 7$  days before/at start, and 3 months (76-104 days) after each test
      - CAB LA PrEP: on-schedule testing defined as receiving an HIV test

≤7 days before/at first injection, and 14 days prior each subsequent injection

- HIV diagnosis: incidence proportion and incidence rates between index date and the 1st discontinuation
- STI testing/screening
  - Assessed during the first period of PrEP use (oral or injectable)
    - Incidence proportion and incidence rate for STI testing/screening for
      - Gonorrhea
      - Chlamydia
      - Syphilis
      - Chancroid
      - Lymphogranuloma venereum
      - *Mycoplasma genitalium*
      - Hepatitis B virus (HBV)
      - Hepatitis C virus (HCV)
      - Genital Herpes (HSV-1, HSV-2)
      - Trichomoniasis
      - Genital Human papilloma virus (HPV) including warts
    - Interval between the first 2 tests for gonorrhea, chlamydia, syphilis done during the first period of PrEP use
      - Testing 3 months (76-104 days) after last test
      - Testing 6 months (168-196 days) after last test
      - Testing 12 months (351-379 days) after last test
- STI diagnoses
  - New diagnosis of STI as noted in medical record or positive test result
  - STI diagnoses for
    - Syphilis
    - Gonorrhea
    - Chlamydia
    - Chancroid
    - Lymphogranuloma venereum
    - *Mycoplasma genitalium*
    - Hepatitis B virus (HBV)
    - Hepatitis C virus (HCV)
    - Genital Herpes (HSV-1, HSV-2)
    - Trichomoniasis
    - Genital Human papilloma virus (HPV) including warts
- Relevant prescription for a selected list of STIs  
 Proportion of STI diagnosis with a prescription within 14 days following diagnosis as follows:
  - Syphilis: benzathine penicillin G, aqueous crystalline penicillin G, procaine penicillin G + probenecid, doxycycline
  - Gonorrhea: ceftriaxone, ceftriaxone + doxycycline, gentamicin + azithromycin,

- cefixime, cefotaxime
- Chlamydia: doxycycline, azithromycin, levofloxacin, amoxicillin
- Chancroid: azithromycin, ceftriaxone, ciprofloxacin, erythromycin base
- Lymphogranuloma venereum: doxycycline, azithromycin, erythromycin base
- *Mycoplasma genitalium*: doxycycline + azithromycin, doxycycline + moxifloxacin
- Trichomoniasis: metronidazole, tinidazole

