#### ◆ Incident HIV diagnosis among CAB LA PrEP users (Objective 3.6)

- HIV diagnosis during periods of CAB LA PrEP use

Describe:

- HIV testing (timing and detailed assay results)
- Adherence to injection schedule
- HIV treatment
- Viral load measurements timing and results and if viral suppression was obtained
- Concomitant STI diagnosis
- HIV drug resistance

- HIV diagnosis after CAB LA PrEP discontinuation

Describe:

- HIV testing (timing and detailed assay results)
- Days between the last CAB LA injection and HIV diagnosis

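### CAB LA use is dated to end 127 days after the last injection and does not stop at a switch, so each discontinued episode counts 60 days beyond the protocol's own coverage as CAB LA time

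*Protocol*

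**What the plan says.** All the relevant rules are in Protocol section 7.3.3.

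- **Coverage (Objective 3.3, Adherence to CAB LA PrEP schedule).** For the first injection, "coverage = 37 days (30 days of coverage + 7-day injection window"). After that, "Subsequent injections: coverage = 67 days (60 days of coverage + 7-day injection window"). Coverage does not stack: "Each calendar day will only be counted once".
- **Recognising discontinuation (Table 3).** The criterion is ">127 days without injection". Days 68–97 are classed as a short delay and days 98–127 as a long delay requiring reinitiation.
- **Dating the end of use (Objective 3.4).** The analysis set is given as "CAB LA PrEP: among complete initiators with at least one maintenance injection". For a discontinuer, continuous time on CAB LA is "days from first initiation injection to discontinuation date (i.e., 127 days after last injection"). The first period of use is otherwise censored at study end, loss to follow-up, death or HIV acquisition. A start of oral PrEP or LEN is not on the list.
- **Rates by modality (Objective 3.5).** HIV diagnosis is reported as "incidence proportion and incidence rates between index date and the" first discontinuation. HIV testing has the same end point, and STI testing is assessed over the first period of use.
- **HIV cases (Objective 3.6).** Cases are divided into "HIV diagnosis during periods of CAB LA PrEP use" and those diagnosed after discontinuation. Days since the last injection are requested only for the second group.

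**The concern.** A long gap is a sound way to recognise that someone has stopped. It does not follow that use continued to the end of the gap. Under the protocol's definitions, days 68–127 after the last injection are uncovered when adherence is calculated but count as CAB LA use when duration and rates are calculated.

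Three outputs are affected:

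- Months on regimen, both first period and cumulative, are lengthened for every discontinuer in the Objective 3.4 set.
- The CAB LA rates of HIV and STI testing and diagnosis take in person-time and events from uncovered days. For those who switch within the gap, they also take in time and events on another product.
- The Objective 3.6 group diagnosed during use mixes covered days with days 68–127.

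In addition, oral bridging is looked for only between discontinuation and resumption, so bridging inside the 127 days can go unrecorded.

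**Working it through.** **Inputs.** Coverage of 37 days (30 + 7) after the first injection and 67 days (60 + 7) after each later one; end of use at last injection + 127 days (all section 7.3.3); 748 CAB LA users (section 7.5).

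**1. The protocol's own figures reproduce.** 127 = 2 × 60 + 7. The time-point windows follow from it: 365 − 127 = 238 and 730 − 127 = 603, the lower bounds stated for 12 and 24 months. Objective 3.4 therefore applies 127 days consistently.

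**2. Excess per discontinued episode.** Everyone in the Objective 3.4 set has had at least one maintenance injection, so the last injection always carries 67 days of coverage. Excess = 127 − 67 = 60 days; 60 / 30.4375 = 1.97 months. Anyone who dies, acquires HIV, is lost or reaches study end before day 127 is censored and is not a discontinuer, so each discontinuer carries the full 60 days. A second discontinued episode adds another 60.

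**3. Relative size on the nominal schedule** (injections on days 0 and 30, then every 60 days). With k maintenance injections the last falls on day 30 + 60k. Recorded duration = last + 127; covered span = last + 67.

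| Maintenance injections | Last injection (day) | Recorded (days) | Covered (days) | Excess |
|---|---|---|---|---|
| 1 | 90 | 217 | 157 | +38% |
| 2 | 150 | 277 | 217 | +28% |
| 4 | 270 | 397 | 337 | +18% |
| 5 | 330 | 457 | 397 | +15% |
| 12 | 750 | 877 | 817 | +7% |

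**4. Effect on a rate.** If no events fall in the added days, a discontinuer's contribution is diluted by 60/217 = 28% (one maintenance injection) to 60/877 = 7% (twelve). If events do fall there, the rate can rise instead.

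**5. Person-time.** The protocol gives no discontinuation share. Assume 20–60% of 748 discontinue once: 150 × 60 / 365.25 = 25 person-years, up to 449 × 60 / 365.25 = 74 person-years. These are upper bounds for the assumed shares, because the Objective 3.4 set is smaller than 748.

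**6. Time-point status.** An injection on day 238 counts as on CAB LA at day 365, although coverage ended on day 238 + 67 = 305. At 24 months, 603 + 67 = 670 against day 730. The gap is again 60 days.

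**The case against.** **Adherence and persistence are different measures.** The 67-day rule serves days covered over the first 12 months; the 127-day rule serves time on regimen, and Table 3 treats days 68–127 as late, not stopped. This stands. A reader might infer that the protocol contradicts itself or that the 127-day threshold is wrong; the text supports neither. What remains is that the end of an allowance for lateness becomes the end date of exposure and is carried into event rates.

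**HIV case timing is already planned.** Section 7.7.1.1 promises an individual timeline of injections and HIV tests for every CAB LA user diagnosed with HIV, and Objective 3.6 asks for adherence to the injection schedule in cases during use. It would therefore be too strong to say that a diagnosis on days 68–127 cannot be located. The timelines do not, however, correct the Objective 3.5 rates or the durations.

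**Moving the end date to day 67 for discontinuers would bring its own bias.** This also stands. Someone diagnosed on day 100 is censored at HIV acquisition and never shows a gap above 127 days, so the event stays in the numerator while HIV-free discontinuers lose days 68–127 from the denominator. Someone injected late, on day 120, would keep days that a discontinuer loses, so exposure would depend on the future. Section 7.9 also concedes that diagnosis timing depends on testing: a diagnosis shortly after day 67 may reflect infection acquired while covered.

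**Reach.** Other-product time arises only for those who switch within the gap, a number the protocol does not give. LEN was approved in June 2025 and the study ends in December 2025, so LEN overlap is confined to the last months. The study is descriptive, with no hypothesis test at stake.

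**Conclusion.** The point holds as a question of how exposure time is dated. Within the Objective 3.4 set, each discontinued episode includes 60 days (about 2.0 months) beyond the protocol's own coverage, and CAB LA time is not ended at a switch. The 60 days follow directly from the protocol's figures. The +38% to +7% range rests on nominal injection timing. The 25–74 person-years rest on an assumed discontinuation share of 20–60% and one discontinuation per user; they are a ceiling, not an estimate.

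Duration is lengthened in one direction. A reader might infer that the CAB LA HIV rate is therefore understated, but the documents do not support a direction: it depends on whether events fall in days 68–127. HIV timing relative to CAB LA use and HIV rates by modality are stated objectives, so the dating rule should be settled before analysis.

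**What to change.** In section 7.3.3, reconcile the coverage, discontinuation and rate definitions as follows. These are analysis definitions only; no injection schedule is proposed.

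1. Keep the gap of more than 127 days to identify discontinuation.
2. For every user, end CAB LA time at the first start of oral PrEP or LEN if that comes earlier.
3. Report months on regimen to the end of protocol-defined coverage alongside the 127-day version.
4. For Objectives 3.5 and 3.6, split both person-time and events by days since last injection: ≤67, 68–127 and >127. Apply this to all users, including late returners and HIV cases, not only those later found to have discontinued. The last band needs follow-up beyond the first discontinuation; Objective 3.4 already defines total follow-up time.
5. Show diagnoses on days 68–127 as their own band and do not reassign them to either side.

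**Cost.** Revised wording, a switch date and a banded person-time derivation from injection and dispensing records already in use; no new data. Durations in the coverage-based version will be 60 days shorter per discontinued episode, or shorter still where a switch comes earlier. Because diagnosis lags infection, the middle band will need a sentence of interpretation.

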  - Proportion of CAB LA PrEP users with at least one maintenance injection who are on CAB LA PrEP at 12 months and 24 months after initiation and at the end of the study period
- 3.5- Described patterns of HIV and other STI testing/screening, diagnosis and STI treatment
- a) Assess the incidence of HIV testing and HIV diagnosis during the first period of PrEP use by PrEP modality
  - b) Estimate the frequency of testing for STI diagnosis and STI diagnosis by PrEP modality
    - in the 6 months preceding PrEP initiation
    - during the first period of PrEP use
  - c) Describe the proportion of diagnosed STI with a relevant antimicrobial prescription
- 3.6- Among CAB LA PrEP users diagnosed with HIV (during CAB LA PrEP use or after CAB LA PrEP discontinuation)
- a) Describe the timing of incident HIV diagnoses relative to timing of CAB LA PrEP usage and testing for HIV
  - b) Describe adherence to PrEP injection schedule, HIV treatment, virologic suppression, concomitant STI diagnosis, and HIV drug resistance

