**a) Oral PrEP**

- Discontinuation: any discontinuation, resumption of oral PrEP after discontinuation  
Two durations will be used to identify discontinuation of oral PrEP:
  - o Oral PrEP prescription not refilled within 30 days of the previous dispensing
  - o Oral PrEP prescription not refilled within 90 days of the previous dispensing
- Duration of oral PrEP use for the first period of use

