## **7.9. Limitations of the research methods**

CAB LA PrEP injections are directly observed in clinical settings; thus, injection records in the EHR provide certainty that PrEP was received and the exact timing of injections. In contrast, oral PrEP use and timing cannot be ascertained with the same level of precision. Oral PrEP dispensing is a proxy for PrEP use. The date of oral PrEP initiation is defined as the first PrEP dispensing date; subsequent PrEP dispensing events are considered renewals.

The identification of incident HIV diagnosis relies on HIV testing being conducted. Therefore, information on incident HIV diagnosis and exact timing may be subject to measurement error.

In addition, detailed behavioral and personal information indicating that an individual could benefit from PrEP is not systematically recorded in the EHR. Thus, Veterans who are not on PrEP but could benefit from PrEP will be identified based on risk factors for HIV acquisition or factors linked to behaviors increasing the risk of HIV acquisition which are generally documented in Veterans health records. This approach may result in identifying a broader group of individuals than if individual detailed behavioral information was available.

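### The Objective 3.5 HIV diagnosis rate keeps 127 days of CAB LA time with no scheduled HIV test in its denominator but leaves out infections from that time that are found after discontinuation; oral PrEP is affected to a different extent.

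*Protocol*

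**What the plan says.** All references are to the Protocol.

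- **Objective.** Section 6, Objective 3.5a: "Assess the incidence of HIV testing and HIV diagnosis during the first period of PrEP use by PrEP modality".
- **Counting window.** Section 7.3.3, Objective 3.5: "HIV diagnosis: incidence proportion and incidence rates between index date and the" first discontinuation. There is no allowance for a test made after that date.
- **End of CAB LA time.** Section 7.3.3, Objective 3.4 b), for Veterans who discontinue: "days from first initiation injection to discontinuation date (i.e., 127 days after last injection".
- **CAB LA test schedule.** Section 7.3.3, Objective 3.5, counts a test as on schedule when done "≤7 days before/at first injection, and 14 days prior each subsequent injection". No test is scheduled after the last injection.
- **Oral PrEP.** Section 7.3.3, Objective 3.4 a), gives two discontinuation rules. The first is "Oral PrEP prescription not refilled within 30 days of the previous dispensing", and the second is the same with 90 days. On-schedule oral tests fall 76 to 104 days after the previous test.
- **After discontinuation.** Objective 3.6 describes CAB LA cases one by one, including "Days between the last CAB LA injection and HIV diagnosis". Objective set 3 has no counterpart for oral PrEP. Objective 1.2 classifies every new HIV diagnosis by whether and how recently PrEP was used.
- **Stated limitation.** Section 7.9: "The identification of incident HIV diagnosis relies on HIV testing being conducted". It adds that timing may be mismeasured, but does not mention the cut at discontinuation.

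**The concern.** HIV becomes visible only when someone is tested. If person-time runs past the last scheduled test and case counting stops where person-time stops, the final stretch adds to the denominator but can add to the numerator only through an off-schedule test or record. The error runs in one direction, downwards. It also differs by modality, because the CAB LA tail is fixed at 127 days and tests follow injections, whereas the oral tail depends on a 30- or 90-day refill rule and a roughly quarterly test schedule. Objective 3.5 does not say which oral rule ends its window. The two rates will be shown by modality, and readers will take each as the incidence of HIV while using PrEP.

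**Working it through.** **Check of the plan's own use of 127 days.** The windows for being on CAB LA at 12 and 24 months open on days 238 and 603: 365 − 127 = 238 and 730 − 127 = 603. Both reproduce, so 127 days is applied consistently.

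**CAB LA discontinuers.** Assume injections on days 0, 30, 90, 150 and so on (the 30- and 60-day coverage in section 7.3.3, Objective 3.3 b), the last test on the day of the last injection, and no off-schedule test. The last of n injections is on day L = 30 + 60(n − 2), person-time is L + 127, and the untested share is 127/(L + 127).

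| Injections | L | Person-time | Untested share |
|---|---|---|---|
| 4 | 150 | 277 | 127/277 = 46% |
| 5 | 210 | 337 | 127/337 = 38% |
| 7 | 330 | 457 | 127/457 = 28% |

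If the last test came 14 days before the last injection, the tail is 141 days and the shares are 51%, 42% and 31%.

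**Whole CAB LA cohort.** The protocol gives no discontinuation rate, so this is a range. With a fraction d discontinuing after person-time T, the others followed for C days, and no tail for those others, the share is 127d/[dT + (1 − d)C].

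- Low end: d = 0.10, T = 517 (8 injections), C = 730. 12.7/(51.7 + 657.0) = 1.8%.
- High end: d = 0.50, T = 217 (3 injections), C = 365. 63.5/(108.5 + 182.5) = 21.8%.

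**Oral PrEP.** Assume that the discontinuation date is day 30 or day 90 after the last dispensing (the protocol does not state it outright) and that the last test was on the day of that dispensing.

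- 30-day rule: the next test is due 76 − 30 = 46 to 104 − 30 = 74 days after discontinuation. None of the 29 window days falls inside the counted period. This remains so if the last test was up to 45 days before the last dispensing, since 76 − 45 = 31 is still after day 30.
- 90-day rule: days 76 to 90 (15 of 29, 52%) fall on or before discontinuation and days 91 to 104 (14 of 29, 48%) after it. Only some users are affected.

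**Candidate remedies in the 5-injection example.** Assume a constant hazard and a test at day 210 but none between then and day 337.

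- Planned rate: cases from 210 days over 337 days, 210/337 = 0.62 of the true rate.
- Person-time ended at the last test: 210/210 = 1.00.
- Person-time ended at the last test, plus cases found at the first test within 104 days after discontinuation: from 337/210 = 1.60 to (337 + 104)/210 = 441/210 = 2.10 times the true rate.

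**The case against.** The strongest reply is that Objective 3.5a concerns diagnosis during the first period of use, not infection acquired in it, and that numerator and denominator share that window. Section 7.9 also concedes that diagnosis depends on testing. As a literal definition the rate is coherent, which is a reason to keep it. But the general caveat does not tell a reader that one end of the window is untested by design, or that this differs by modality.

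Other points on that side stand and limit the finding:

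- A reader might infer that oral cases found after discontinuation are reported nowhere. The documents do not support that. Objective 1.1 counts new diagnoses by calendar year, and Objective 1.2 classes these cases by recency of PrEP use. What is missing is narrower: the stated categories do not separate oral from CAB LA, they give no time since last dispensing, and the cases enter no oral PrEP rate.
- CAB LA cases are lost from the rate, not from the report, because Objective 3.6 describes them.
- The 46%, 38% and 28% are not the bias in the reported rate. They are shares of person-time, among discontinuers only, with no off-schedule test.
- Some diagnoses in the tail will be counted. Section 7.3.3 accepts confirmed antibody tests, viral load or a problem-list entry at any time in the window. Section 5 says that HIV must be excluded by testing before PrEP is started, so a Veteran moving to oral PrEP within the 127 days should be tested inside them.
- It is tempting to add that infection is most likely in this stretch because adherence has lapsed. Nothing in the protocol supports that, and the finding does not need it.

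**Conclusion.** The point holds in a limited form. For CAB LA discontinuers with no off-schedule test, the Objective 3.5 rate retains 127 days (up to 141 if the last test preceded the last injection by 14 days) in which an infection can be acquired but is not scheduled to be found. The rate therefore understates HIV incidence during PrEP use. The cohort-wide share of about 2% to 22% of CAB LA person-time rests on an assumed 10% to 50% discontinuing, on-schedule injections and no tail for continuing users; off-schedule tests lower the resulting bias. For oral PrEP the mechanism applies under the 30-day rule when test and last dispensing are close together, and to only part of the users under the 90-day rule. It would be wrong to conclude that all oral users are affected, or that the cases vanish from the study. A difference between the two modality rates could partly reflect where each period ends relative to its last test.

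**What to change.** Keep the planned rate. For both modalities, add a sensitivity rate whose at-risk time runs from index to the last HIV test within the first period of use, or to the diagnosing test if it falls in that period, with cases counted over exactly the same window. Under a constant hazard, with test timing unrelated to infection, this removes the mismatch.

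Do not add diagnoses made after discontinuation to that rate. They come from time already removed from the denominator, which reverses the error (1.60 to 2.10 times the true rate in the example). They may also include infections acquired after use ended. List them separately for oral users, with days since last dispensing, as Objective 3.6 does for CAB LA. State which oral discontinuation rule closes the Objective 3.5 window, or report the rate under both, and name the untested tail in section 7.9.

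The cost is one extra rate per modality and one short listing, from test, dispensing and injection dates that the study already uses. Veterans with no test after index contribute no time to the added rate, so it is slightly less precise than the planned one.
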